OFFICIAL TITLE OF THE STUDY :

EFFECT OF OPTIC NERVE DIAMETER IN TYMPANOPLASTY SURGERY PERFORMED IN LATERAL HEAD POSITION UNDER GENERAL ANESTHESIA

NCT number (not available)

Document Date: 2020-01-12

RESEARCH PROTOCOL

Official Title:

EFFECT OF OPTIC NERVE DIAMETER İN TYMPANOPLASTY SURGERY PERFORMED İN LATERAL HEAD POSITION UNDER GENERAL ANESTHESİA

Research basis and rationale:

Ultrasonography for optic nerve diameter (ONSD) measurement is a non-invasive, rapid, and easily applicable method for diagnosing intracranial pressure changes. In tympanoplasty surgery cases, the head and neck remain in a lateral position, and venous return can sometimes be compressed in the surgical field due to the procedure

Research objective:

The aim of this study is to determine the effect of lateral head position and variables such as demographic data and surgical duration on the increase in intracranial pressure.

Research methodology:

Patients over 18 years of age with ASA I and II who were to undergo tympanoplasty surgery in lateral head and neck position under general anesthesia(GA) were included. Patients' perioperative vital signs (arterial blood pressure, heart rate, sPO2, and EtCO2) were monitored routinely in the operating room. Demographic data (age, gender, weight, height), surgical duration, and perioperative complications were also recorded. Anesthesia was administered with propofol 2-4 mg/kg, rocuronium 0.6 mg/kg, and fentanyl 1-2 mcg/kg for induction, and sevoflurane for maintenance. Following intubation, ONSD measurements were taken in three time intervals by the anesthesiologist: transverse and sagittal planes. Both ONSDs were recorded by ultrasound at T1: 5 min in supine position, T2: end of the procedure with head in lateral position, and T3: supine position before extubation. Postoperative headache and neck pain were questioned upon awakening, and at 1, 6, and 24 hours.

Statistical methodology:

Data were analyzed using Jamovi software (version 2.6.24). Descriptive statistics are presented as mean \pm standard deviation (SD) for continuous variables and as frequencies and percentages for categorical variables.

For the primary outcome, optic nerve sheath diameter (ONSD) measurements obtained at three time points (T1: post-intubation, T2: lateral head position during surgery, T3: supine position before extubation) were analyzed using repeated measures analysis of variance (ANOVA). Post-hoc pairwise comparisons were conducted to identify specific differences between time points, with

Bonferroni correction applied for multiple comparisons.

To investigate factors affecting ONSD changes, the relationship between surgical duration and temporal ONSD variations was examined. Patient age, body mass index (BMI), and surgical side (right vs. left ear) were also evaluated for their effects on ONSD.

To compare ONSD changes between ipsilateral and contralateral eyes relative to the surgical side, a mixed-design ANOVA was performed with Time (3 levels: T1, T2, T3) and Eye (2 levels: right, left) as within-subjects factors and Surgical Side (2 levels: right ear, left ear) as a between-subjects factor.

Statistical significance was set at $p < 0.05$ for all analyses.

An a priori power analysis was performed using G*Power (version 3.1.9.7) for a repeated measures ANOVA with time as the within-subject factor (three measurements). Effect size estimation was based on pilot data (mean ONSD values: 5.27, 5.57, and 5.40 mm), yielding an estimated effect size of $f = 0.45$. Assuming an α level of 0.05, a power of 0.95, three repeated measurements, and a correlation among repeated measures of 0.5, the minimum required sample size was calculated as 18 patients.

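### The primary ONSD reading has no described masking, so a reading shift specific to T2 cannot be told apart from a head-position effect; masked caliper reading of saved frames by the same operator would reduce this risk

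*Combined protocol and SAP*

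**What the plan says.** The Research methodology section states that "ONSD measurements were taken in three time intervals by the anesthesiologist", in two planes by ultrasound. T1 is taken supine after intubation; the other two are given as "T2: end of the procedure with head in lateral position, and T3: supine position before extubation". Each time point is therefore tied to a head position.

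The Statistical methodology section makes ONSD at T1, T2 and T3 the primary outcome. It is tested by repeated measures ANOVA over time, with pairwise follow-up and "Bonferroni correction applied for multiple comparisons". A further mixed-design ANOVA (Time, Eye, Surgical Side) compares the eye on the operated side with the other eye.

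The sample size uses pilot data ("mean ONSD values: 5.27, 5.57, and 5.40 mm"), f = 0.45, α = 0.05, power 0.95, three measurements and a correlation of 0.5, giving a minimum of 18 patients.

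Neither section says whether images are stored, when the calipers are placed, whether the person placing them is masked, how many operators take part, or how repeatable the readings are.

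**The concern.** ONSD is obtained by placing calipers on an image, and the result depends on the operator. Whoever scans can see whether the head is turned. The expected direction is also known: the stated objective refers to a rise in intracranial pressure, and the pilot mean is highest at T2.

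An error that is the same at all three times cancels in a within-patient comparison. An error that differs at T2 does not. Every patient follows the same T1, T2, T3 sequence, so such an error has the same pattern over time as the effect under test. No step of the primary analysis could separate the two afterwards. At stake is a significant time effect, or an enlarged one, that comes partly from reading rather than from position.

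**Working it through.** **1. The plan's own sample size.** For a within-subject factor, λ = f²·N·m/(1−ρ), with df = m−1 and (N−1)(m−1). With f = 0.45, N = 18, m = 3 and ρ = 0.5:

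λ = 0.2025 × 18 × 3 / 0.5 = 21.87, df 2 and 34, power 98.5%.

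Under sphericity, 95% power is reached at N = 15. The stated 18 is obtained with a nonsphericity correction of 0.75 (power 95.6%), which the plan does not mention. The figure is not reproduced exactly from the stated inputs, but it errs on the safe side, and nothing below depends on how it arose.

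**2. The SD implied by the plan.** The documents give no SD. The pilot means average 16.24/3 = 5.413 mm, with deviations −0.143, +0.157 and −0.013. Their SD (divisor 3) is √(0.04527/3) = 0.1228 mm. Since f = SD of means / common SD, the common SD is 0.1228/0.45 = 0.273 mm.

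**3. A T2 shift with no true effect.** Let the true means be equal and let T2 be over-read by b on average. The recorded means then differ by (0, b, 0), whose SD is b·√2/3, so f_b = 0.4714·b/SD. For SD 0.273 mm, ρ = 0.5 and N = 18, λ = 108·f_b²:

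- b = 0.05 mm: f_b = 0.086, λ = 0.81
- b = 0.10 mm: f_b = 0.173, λ = 3.22
- b = 0.15 mm: f_b = 0.259, λ = 7.25
- b = 0.20 mm: f_b = 0.345, λ = 12.9

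**4. Chance that the omnibus test is significant at 0.05** (noncentral F, df 2 and 34). The nominal rate is 5%.

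| Assumed T2 over-reading | SD 0.273, ρ 0.5 | SD 0.273, ρ 0.7 | SD 0.4, ρ 0.5 | SD 0.5, ρ 0.5 |
|---|---|---|---|---|
| 0.05 mm | 11% | 15% | 8% | 7% |
| 0.10 mm | 32% | 50% | 17% | 12% |
| 0.15 mm | 63% | 85% | 33% | 22% |
| 0.20 mm | 88% | 98% | 54% | 37% |

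The over-readings, the SDs of 0.4 and 0.5 mm and the correlation of 0.7 are assumptions. A larger SD lowers the figures and a higher correlation raises them.

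**5. The pairwise test.** For T2 against T1 at 0.05/3, the SD of the difference is 0.273·√(2 × 0.5) = 0.273 mm. With b = 0.15 mm the noncentrality is (0.15/0.273)·√18 = 2.33, and the test is significant in about 40% of trials (64% at ρ = 0.7).

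**6. Scale.** The pilot change from T1 to T2 is 5.57 − 5.27 = 0.30 mm. A shift of 0.15 mm is half of that and 0.15/5.27 = 2.8% of the T1 mean. Reproducing the whole pilot change would need 0.30 mm.

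**7. The eye-by-side analysis.** A T2 over-reading equal in both eyes cancels in the ipsilateral-contralateral contrast over time. It does not cancel in the primary time effect.

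**The case against.** The strongest reply is that the documents do not say the calipers were read unmasked. They say who took the measurements, not when the calipers were placed or whether images were kept. In a protocol this short, silence shows only that masking is not described. That stands. Head position is evident during scanning, but unmasked caliper placement is an inference, and one sentence from the sponsor could settle it.

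Second, the sizes are assumed. The documents give no measurement-error figure and the SD is back-calculated. A shift of 0.05 mm raises the error rate only to 11%. This also stands, and it is why a range is given. But the documents offer nothing that would rule out 0.10 or 0.15 mm.

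Third, masked re-reading does not reach probe plane, pressure or frame choice, all set by someone who can see the head, and the same person may recall images. That is correct, and it limits the remedy to caliper placement.

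Fourth, a reader might infer that a control group would have solved the problem. The documents do not support that: an operator who sees the head position would see it in a control group too. The eye-by-side contrast does resist a shift shared by both eyes, but it answers a different question from the primary one.

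**Conclusion.** The point holds in a limited form. No masking is described for an operator-dependent primary outcome whose time points are marked by visible head position, and the planned primary analysis cannot separate a T2-specific reading shift from a position effect. Under the plan's own f and correlation, with 18 patients and no true effect, assumed shifts of 0.05, 0.10 and 0.15 mm give about 11%, 32% and 63% significant omnibus tests. For 0.15 mm the range is about 22% (SD 0.5 mm, correlation 0.5) to 85% (SD 0.273 mm, correlation 0.7).

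Two stronger conclusions are tempting and are not supported. One is that a small reading bias could explain the pilot effect: a shift of 0.05 to 0.15 mm can yield a significant p-value, but the full pilot change needs 0.30 mm. The other is that such a bias occurred: the documents contain no evidence of its presence or size.

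**What to change.** Add to the Research methodology section a step such as:

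> Each ONSD frame at T1, T2 and T3 is saved without caliper marks. The same operator later places the calipers on all frames in random order, with patient and time labels hidden. These readings are the primary data. Readings made at the time of scanning are analysed as a sensitivity analysis.

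Comparing the two sets of readings by time point would show how far the numbers move once the labels are hidden. The protocol should also state that acquisition remains unmasked and that images may be recalled, so the bias is reduced rather than removed.

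The cost is image storage, coding of the frames and re-measurement time: 18 patients × 3 times × 2 eyes × 2 planes = 216 frames, assuming the minimum sample and one frame per eye, plane and time. No additional reader, scan or patient is needed, and the sample size does not change.

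The protocol is written in the past tense. If scanning is finished and frames were kept, the re-reading can still be done. If they were not kept, unmasked reading should be reported as a limitation of the primary result. If the reading was in fact masked, the protocol should say so.

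### Both planned ANOVAs drop any patient with an empty cell and no missing-scan rule is given; mixed models on all valid scans would keep those patients' other readings

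*Combined protocol and SAP*

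**What the plan says.** Under Statistical methodology, the primary ONSD measurements at three time points "were analyzed using repeated measures analysis of variance (ANOVA"), followed by Bonferroni-corrected pairwise comparisons. For the two eyes, "a mixed-design ANOVA was performed with Time (3 levels: T1, T2, T3) and Eye (2 levels: right, left) as within-subjects factors", with "Surgical Side (2 levels: right ear, left ear) as a between-subjects factor". The term mixed-design here means within-patient plus between-patient factors. It does not mean a mixed-effects model.

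Under Research methodology, the first scan is described as "Both ONSDs were recorded by ultrasound at T1: 5 min in supine position", and the later two as "T2: end of the procedure with head in lateral position, and T3: supine position before extubation". The text also says that "ONSD measurements were taken in three time intervals by the anesthesiologist: transverse and sagittal planes". It does not say how the two eyes and two planes are reduced to the value used in the primary ANOVA.

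The sample size of 18 is presented as a minimum and assumes "a power of 0.95, three repeated measurements, and a correlation among repeated measures of 0.5", with f = 0.45. There is no rule for a missing scan, no definition of the analysis set, no imputation or alternative model, and no allowance for loss.

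**The concern.** A classical repeated measures ANOVA needs a full set of within-patient cells. One missing time point removes the patient from the primary analysis. One missing reading out of six removes the patient from the Time x Eye x Surgical Side analysis. A patient who misses T3 would therefore also lose a valid T1-to-T2 change, which is the contrast closest to the stated aim of measuring the effect of lateral head position.

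The later scans are the more exposed ones. T2 is taken with the head turned, and T3 has to fit between the return to supine and extubation.

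Two things are at stake. The first is precision in a small study. The second is bias: if loss of T3 is related to the T2 reading, the patients left in the complete-case analysis are a selected group. The two ANOVAs could also end up on different sets of patients.

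**Working it through.** **Inputs from the plan:** pilot means 5.27, 5.57 and 5.40 mm; f = 0.45; correlation 0.5; three measurements; alpha 0.05; power 0.95; N = 18. The SD of the three means is 0.1228 mm, so f = 0.45 implies a within-time SD of 0.1228 / 0.45 = 0.273 mm. The plan states no SD. **Assumed:** the loss rate q, because the plan gives none.

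**1. The plan's own figure.** For one group, lambda = f²·N·m / (1 − rho), with 2 and 2(N − 1) degrees of freedom under sphericity (epsilon = 1).
- N = 15: lambda = 0.2025 × 15 × 3 / 0.5 = 18.2, power 0.960. This is the smallest N that reaches 0.95.
- N = 18: lambda = 0.2025 × 18 × 3 / 0.5 = 21.9, power 0.985.

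So 18 is conservative on the stated inputs. It is matched exactly with epsilon = 0.75 (power 0.956), which the plan does not state. Under epsilon = 1 there is some slack for lost patients. Under epsilon = 0.75 there is almost none: N = 17 gives 0.944.

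**2. Expected complete patients out of 18.**

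| Assumed loss q | Only T2 and T3 at risk, both eyes lost together: 18(1 − q)² | Every scan independently at risk, three time points: 18(1 − q)³ | Every scan independently at risk, six readings: 18(1 − q)⁶ |
|---|---|---|---|
| 2% | 17.3 | 16.9 | 15.9 |
| 5% | 16.2 | 15.4 | 13.2 |
| 10% | 14.6 | 13.1 | 9.6 |

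The first column applies to both ANOVAs, because losing a time point for both eyes empties the same patient in each. At 5% independent loss, the six-reading analysis uses 13.23 × 6 = 79.4 readings. A model on all valid scans uses 0.95 × 108 = 102.6.

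**3. Primary power for Time.** This was simulated with N = 18, the pilot means, SD 0.273 and rho 0.5. All three time points were at risk independently and completely at random, with 3,000 runs per setting. The mixed model had a random patient intercept fitted by REML.

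| q | Complete-case ANOVA | Mixed model, all scans |
|---|---|---|
| 0 | 0.982 | 0.982 |
| 2% | 0.976 | 0.983 |
| 5% | 0.957 | 0.972 |
| 10% | 0.917 | 0.967 |
| 20% | 0.768 | 0.933 |

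Type I error was 0.046 to 0.056 for both methods. Repeat simulations put the mixed model at 10% loss at 0.96. If only T2 and T3 are at risk, 10% loss leaves about 14.6 patients. The formula in step 1 gives 0.945 at N = 14 and 0.960 at N = 15, so complete-case power is then roughly 0.95.

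**4. Bias, illustrative.** Suppose half of the patients in the top quarter of T2 readings miss T3 (0.5 × 0.25 = 12.5% of patients).
- The mean standardised T2 in the top quarter of a normal distribution is 0.3178 / 0.25 = 1.271.
- The patients who remain average −(0.125 × 1.271) / 0.875 = −0.182 SD at T2, or −0.182 × 0.273 = −0.050 mm.
- With rho = 0.5, their T1 and T3 means are each lower by 0.025 mm.
- The complete-case rise is 0.30 − 0.050 + 0.025 = 0.275 mm.
- The complete-case fall is 0.17 − 0.050 + 0.025 = 0.145 mm.

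A likelihood estimate using all observed readings recovers 0.300 and 0.170 mm when the correlations really are equal.

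**5. Which mixed model.** Two checks show that the covariance structure matters.
- With assumed correlations of 0.3 (T1-T2), 0.7 (T2-T3) and 0.5 (T1-T3) in the same scenario, a random-intercept model estimated the fall as 0.182 mm against a true 0.170. Complete-case analysis gave 0.154. The random intercept alone therefore does not guarantee an unbiased fall.
- For laterality, a model with only patient and eye-within-patient effects was simulated on complete data with no Time effect. With patient-by-time variance assumed at 20% and 30% of the total, its type I error for Time was 0.115 and 0.150. The planned ANOVA gave 0.051 and 0.049. A patient-by-time effect has to be in the model.

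**The case against.** The strongest reply is that the loss is hypothetical. All three scans fall within one anaesthetic session and are taken by the anesthesiologist, and the protocol describes the technique as quick and easy. T3 is defined as preceding extubation. There is no follow-up visit from which patients could drop out, and 18 is a minimum rather than the enrolled number. All of this stands. A reader might infer that scans were in fact lost, or that the study is underpowered. The documents support neither: they report no loss, and on the stated inputs with epsilon = 1, primary power still meets 0.95 at 5% loss.

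A reader might also infer that one unreadable eye removes a patient from the primary analysis. That is shown only for the Time x Eye x Surgical Side ANOVA. For the primary ANOVA it depends on how the eyes are combined, which is not stated. The counts of 13.2 and 9.6 likewise need the two eyes to be lost independently. An early extubation would lose both eyes at once, and the two analyses would then keep the same patients.

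Finally, a mixed model is not a cure-all. It does not correct for loss that depends on the unseen ONSD, and a badly chosen covariance structure can do harm. That is a reason to specify the structure carefully. It does not justify leaving missing scans unaddressed.

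**Conclusion.** The point holds as a statement about method and as a low-cost improvement. Both named ANOVAs use only complete patients, at three time points for the primary and six readings for laterality, and nothing in the plan offsets this.

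The size depends on an assumed loss rate. Between the narrower and wider assumptions, 5% loss leaves 16.2 to 15.4 of 18 patients in the primary analysis and 16.2 to 13.2 in the laterality analysis. At 10% the ranges are 14.6 to 13.1 and 14.6 to 9.6. With all three time points at risk, primary power is about 0.96 at 5% and about 0.92 at 10%, against 0.96 to 0.97 at 10% with all scans. These power figures assume sphericity and the implied SD of 0.273 mm.

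The bias is a separate matter from power, and a larger sample would not remove it. It arises only if loss of T3 is related to the T2 reading. The 0.025 mm in the example is illustrative and should not be read as an estimate for this study. With few or no missed scans, there is little or nothing to gain.

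**What to change.** Analyse every valid scan with linear mixed models fitted by REML, using Kenward-Roger or Satterthwaite degrees of freedom.

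- **Primary:** Time as a fixed effect with an unstructured covariance over the three times. Alternatively, use a random patient intercept and state that it assumes equal correlations. Keep the Bonferroni-corrected pairwise contrasts, and state how eyes and planes are combined into the analysed value.
- **Laterality:** Time x Eye x Surgical Side as fixed effects, with random patient, eye-within-patient and patient-by-time effects.
- **Reporting:** give the number of scans missing at each time point with the reasons, and keep the planned ANOVAs as a complete-case sensitivity analysis.

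The cost is some added wording, slightly more analysis work and a missing-at-random assumption. With complete data, the random-intercept version gives the same primary Time test as the planned ANOVA. The unstructured version is closer to the multivariate test, whose power at N = 18 is 0.974 against 0.985, a small price for not assuming equal correlations. No further patients, scans or procedures are needed. Because the plan is written in the past tense, the change can also be applied to scans already collected.

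### Holm instead of Bonferroni for the three pairwise time comparisons keeps the 5% family-wise bound and, on the plan's inputs, raises T2 vs T3 power from about 51% to 63%; T1 vs T2 is essentially unchanged

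*Combined protocol and SAP*

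**What the plan says.** The Statistical methodology section of the combined protocol and SAP analyses ONSD at T1, T2 and T3 by repeated measures ANOVA. It continues: "Post-hoc pairwise comparisons were conducted to identify specific differences between time points", with "Bonferroni correction applied for multiple comparisons". The general level is given as "Statistical significance was set at $p < 0.05$ for all analyses". Three time points make three pairs, so Bonferroni tests each at 0.05/3 = 0.0167. No pair is ranked above the others, and neither a step-down method nor confidence intervals are mentioned.

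The power paragraph of the same section rests on pilot data ("mean ONSD values: 5.27, 5.57, and 5.40 mm"), an effect size f of 0.45, alpha 0.05, power 0.95 and a correlation of 0.5. It concludes that "the minimum required sample size was calculated as 18 patients". It gives no pilot SD and no power for any single pair.

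The Research methodology section defines the later two measurements as "T2: end of the procedure with head in lateral position, and T3: supine position before extubation". T2 vs T3 is therefore one of the two lateral-versus-supine contrasts; the other is T1 vs T2.

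**The concern.** Bonferroni holds every pair to 0.0167 even after another pair has been rejected. Holm compares the smallest p-value with 0.0167, the next with 0.025 and the largest with 0.05, and stops at the first failure. It controls the family-wise error at the same 5% under any dependence between the tests. Keeping Bonferroni therefore gives up power without a tighter error bound.

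The loss matters most when one difference is large and the others are modest, which is what the pilot means suggest. The pairwise tests are how the plan locates the change in time. At stake is the chance of showing that ONSD falls when the head returns to supine (T2 vs T3) and that it remains above baseline (T1 vs T3). The stated 0.95 power refers to the omnibus test, so no stated power is missed.

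**Working it through.** **The plan's sample size.** For a within-subject factor under sphericity, λ = N·m·f²/(1 − ρ), with 2 and 2(N − 1) degrees of freedom. At N = 18, λ = 18 × 3 × 0.2025/0.5 = 21.87 and power is 98.5%. The written inputs reach 95% at N = 15 (96.0%). A nonsphericity factor of 0.75, which the plan does not state, would give exactly 18 (95.6%). The stated 18 is thus conservative for the omnibus test; it is used below as given.

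**Implied SD (assumption).** The mean of 5.27, 5.57 and 5.40 is 5.413. The squared deviations sum to 0.04527. With divisor 3 the SD of the means is √0.01509 = 0.1228, so σ = 0.1228/0.45 = 0.273 mm. If f had been formed with divisor 2, σ = 0.1504/0.45 = 0.334 mm.

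**Standardised differences.** The SD of a paired difference is σ√(2(1 − ρ)), which equals σ at ρ = 0.5. Hence:

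- T1 vs T2: 0.30/0.273 = 1.099
- T2 vs T3: 0.17/0.273 = 0.623
- T1 vs T3: 0.13/0.273 = 0.476

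**Power at n = 18, two-sided paired t-tests.** Bonferroni power comes from the noncentral t distribution with 17 df, noncentrality d√18, at level 0.0167. For T2 vs T3 the noncentrality is 0.623 × 4.243 = 2.64. Holm power comes from 200,000 simulated trivariate-normal trials.

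| Pair | Bonferroni | Holm |
|---|---|---|
| T1 vs T2 | 96.9% | 97.1% |
| T2 vs T3 | 51.0% | 62.5% |
| T1 vs T3 | 29.4% | 42.1% |

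As a check, exact power for T2 vs T3 is 58.1% at level 0.025 and 70.2% at 0.05; the Holm figure lies between them, as it should. All three pairs are significant in 9.8% of trials with Bonferroni and 26.2% with Holm.

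**Sensitivity of T2 vs T3 (Bonferroni / Holm).**

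| Assumed SD | ρ = 0.3 | ρ = 0.5 | ρ = 0.7 |
|---|---|---|---|
| 0.273 mm | 36.4 / 45.5% | 50.9 / 62.5% | 76.6 / 87.4% |
| 0.334 mm | 23.5 / 29.3% | 33.7 / 42.3% | 56.1 / 68.3% |

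The smallest gain is 29.3 − 23.5 = 5.8 points and the largest 68.3 − 56.1 = 12.2 points. Requiring a significant omnibus F first leaves the headline unchanged (51.1 / 62.7%). Using the pooled ANOVA error term with 34 df gives 55.4 / 66.5%.

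**Sample size for 80% power on T2 vs T3** (SD 0.273 mm, ρ = 0.5). Bonferroni gives 78.4% at 29 and 80.1% at 30. Holm gives 79.7% at 24 and 81.7% at 25. The difference is 30 − 25 = 5 patients.

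**Error control.** With no true differences, any false rejection occurs in 4.6% of trials under both methods. If ONSD rises and stays up (5.27, 5.57, 5.57), a false T2 vs T3 rejection occurs in 1.7% with Bonferroni and 4.8% with Holm, still within 5%.

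**The case against.** The strongest reply is that nothing is broken. Bonferroni is valid and gives simple matching simultaneous confidence intervals, which Holm does not. The objective speaks of an increase in intracranial pressure, and the contrast nearest to that, T1 vs T2, gains almost nothing. The size of the gain rests on a back-calculated SD. The plan also does not say how two eyes and two planes become the analysed ONSD, so SD and correlation are uncertain. Finally, the text is in the past tense, so a free change may no longer be possible.

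Most of this stands as a limit on weight. The range of 6 to 12 points belongs to the grid shown and is not a bound: at SD 0.273 mm the gain is about 5 points at ρ = 0.8 and near zero at ρ = 0.9; it is about 3 points at an SD of 0.50 mm and up to 14 under some unequal correlations. The reply does not touch the main statement that Holm dominates Bonferroni for testing at the same 5% bound, which needs no assumed SD. Nor does the plan rank T1 vs T2 above the other pairs. The headline figure depends only on the ratio of the mean differences to the SD, which f = 0.45 and the pilot means fix once the usual divisor-3 definition of f is taken.

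**Conclusion.** The point holds as an optional improvement, not as a fault. That Holm is never less powerful than Bonferroni at the same family-wise bound is certain. The size of the benefit depends on the assumptions: about 12 points for T2 vs T3 and 13 for T1 vs T3 at SD 0.273 mm, correlation 0.5, n = 18 and two-sided paired tests. Across the grid above, T2 vs T3 power runs from 24 to 77% with Bonferroni and from 29 to 87% with Holm. At the headline inputs Holm still leaves T2 vs T3 short of 80% with 18 patients. Because 18 is a minimum, a larger enrolment shifts the figures: at n = 24 they are 68% and 80%.

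**What to change.** If results have not been seen, replace the Bonferroni correction with *Holm (step-down Bonferroni) correction* for the three pairwise time comparisons. Report each mean difference with a 95% CI and state whether the interval is adjusted for multiplicity.

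If results have been seen, keep Bonferroni as the planned analysis and show Holm beside it as a labelled additional analysis, not as a silent replacement.

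The first route costs one word, the second one disclosed extra analysis. Two trade-offs should be accepted knowingly. Intervals that match Holm are harder to construct, and unadjusted intervals can disagree with Holm decisions. Holm also uses more of the permitted 5% when some differences are truly zero.

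### Does the mixed ANOVA need a named interaction and an interval before it can answer the ipsilateral-versus-contralateral question?

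*Combined protocol and SAP*

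**What the plan says.** All the relevant text is in the Statistical methodology section of the combined protocol and SAP.

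- The purpose is "To compare ONSD changes between ipsilateral and contralateral eyes relative to the surgical side".
- The model is a mixed-design ANOVA "with Time (3 levels: T1, T2, T3) and Eye (2 levels: right, left) as within-subjects factors and Surgical Side", the last being a two-level between-patient factor for the operated ear.
- Separately, among the factors that may affect ONSD, "surgical side (right vs. left ear) were also evaluated for their effects on ONSD".
- The only decision rule is "Statistical significance was set at $p < 0.05$ for all analyses".
- The post-hoc tests described belong to the primary analysis: "Post-hoc pairwise comparisons were conducted to identify specific differences between time points".
- The sample size was computed "for a repeated measures ANOVA with time as the within-subject factor (three measurements)" and so covers the Time effect alone.

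The section does not say which term of the mixed model decides the laterality question. It plans no ipsilateral-minus-contralateral estimate and no confidence interval.

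**The concern.** The question is about ipsilateral and contralateral eyes, but the model has no such factor. Eye is right or left, so which eye is ipsilateral depends on the operated ear. The fit gives seven terms (three main effects, three two-way interactions, one three-way), and none is named as the test. Time × Eye looks like the natural place to ask whether the two eyes change differently, yet it does not answer the question. An analyst who read it could report no difference between eyes when one exists.

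A second worry is interpretation. The study was sized for Time, so a p-value above 0.05 on the laterality term, reported without an interval, might be taken to mean that both eyes change alike.

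**Working it through.** **1. The plan's own figure.** With f = 0.45, alpha 0.05, power 0.95, three measurements and correlation 0.5, use noncentrality λ = f² × n × 3 / (1 − 0.5). Under sphericity the smallest n is 15 (power 0.960), and n = 18 gives 0.985. The stated 18 appears if a nonsphericity correction of 0.75 is assumed (power 0.956), which the plan does not mention. The stated number is therefore on the cautious side, and nothing below depends on how it was reached.

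**2. Which term carries the answer.** Take the pilot means 5.27, 5.57 and 5.40 mm and add an illustrative 0.30 mm to the ipsilateral eye at T2 only.

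| Patients | Eye | T1 | T2 | T3 |
|---|---|---|---|---|
| Right ear | right (ipsilateral) | 5.27 | 5.87 | 5.40 |
| Right ear | left | 5.27 | 5.57 | 5.40 |
| Left ear | right | 5.27 | 5.57 | 5.40 |
| Left ear | left (ipsilateral) | 5.27 | 5.87 | 5.40 |

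- Averaged over the two sides, each eye has T2 mean (5.87 + 5.57)/2 = 5.72, so Eye and Time × Eye are exactly 0.
- Averaged over eyes, each side also has 5.72 at T2, so Surgical Side and Time × Surgical Side are exactly 0.
- Eye × Surgical Side is ±(0.30/3)/2 = ±0.05. This is the laterality of the average level, not of change.
- Time × Eye × Surgical Side has size 0.30/2 − 0.05 = 0.10 at T2 and 0 − 0.05 = −0.05 at T1 and T3, with signs reversed for the contralateral eye.

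Only the three-way term carries laterality of change.

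**3. The planned coding gives the right quantity.** Let L be the ipsilateral-minus-contralateral difference in change and a any general right-left asymmetry in change. The right-minus-left change is a + L in right-ear patients and a − L in left-ear patients. Half the difference is L, and a drops out. In a simulated data set with a 12:6 split, recoding Eye as ipsilateral/contralateral while keeping Surgical Side gave the same results: t = 2.762 for the T2−T1 contrast and F(2,32) = 3.874 under both codings.

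**4. What misreading would cost.** Assume a true 0.2 mm laterality effect, SD 0.273 mm for the between-eye difference in change, and N = 18. In simulation, Time × Eye with Type III tests rejects 5% of the time at every split tried. The 1-df T2−T1 contrast within the three-way term rejects 83% at 9:9 and 79% at 12:6. The 2-df interaction itself, at 9:9 and with equal correlations over time, has power 0.87 if the effect is absent or fully present at T3, and 0.76 if half of it remains.

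**5. Precision at N = 18.** The root mean squared deviation of the pilot means is 0.1228, so the implied SD is 0.1228/0.45 = 0.273 mm. With correlation 0.5, the SD of a change is 0.273 × √(2 × 0.5) = 0.273 mm. For between-eye correlation r (not in the documents), the SD of the difference in change is 0.273 × √(2(1 − r)). The half-width is 2.120 × SD × √(1/n₁ + 1/n₂)/2, where 2.120 is the t quantile on 16 df.

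| r (assumed) | SD, mm | Half-width 9:9 | Half-width 12:6 |
|---|---|---|---|
| 0.2 | 0.345 | 0.17 | 0.18 |
| 0.5 | 0.273 | 0.14 | 0.15 |
| 0.8 | 0.173 | 0.09 | 0.09 |

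If 0.273 mm is instead the SD of a two-eye average, the 9:9 half-widths become 0.22, 0.16 and 0.09 mm.

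**The case for a change.** The best case for a change is that it costs almost nothing. One reworded sentence would name the test, remove the temptation to read Time × Eye, and put an interval beside a p-value from a sample not sized for that question. The algebra behind this is correct, and so is the remark that the plan names neither term nor estimate.

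It stands as a point of clarity only. Change requires Time, and ipsilateral versus contralateral requires Eye crossed with Surgical Side. The sentence that states the aim lists exactly those three factors, so the term can be deduced even though it is not written out. With one term answering the question, the count of seven creates no multiplicity problem for it. The plan makes no claim that the eyes behave alike, so the warning about a non-significant result addresses an inference it does not propose. Sizing on Time is ordinary, since that is the primary analysis, and the absence of intervals runs through the whole section rather than marking this analysis out. The numbers of right-ear and left-ear operations already fall under the planned frequencies and percentages.

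Tighter wording can also do harm. Declaring all other terms descriptive would demote the separately planned evaluation of surgical side. Reporting only the T2−T1 difference beside a 2-df interaction would let test and estimate disagree. Dropping Surgical Side and pooling would lose the cancellation in step 3: with no laterality effect and an assumed 0.2 mm right-left asymmetry, the pooled contrast rejects 8% of the time at 12:6 and 25% at 14:4, against 5% for the contrast with Surgical Side kept.

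**Conclusion.** No change follows. The planned model is valid for its stated aim, includes the one term that answers it, and is protected against a right-left asymmetry. Anyone who carries out the plan as written obtains a sound test. What is missing is explicit wording that an analyst can be expected to supply: reading Time × Eye × Surgical Side and, in the report, giving the between-eye difference in both T2−T1 and T3−T1 change in mm with 95% intervals.

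The conclusion about the term is algebraic and rests on no assumption. The size does not share that standing. A half-width of about 0.09 to 0.18 mm (roughly 29% to 61% of the 0.30 mm pilot rise) assumes a between-eye correlation of 0.2 to 0.8, compound symmetry, a per-eye reading of the pilot SD, and splits of 9:9 or 12:6. The plan gives only the 0.5 correlation among repeated measures.
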